7.5 Follow-Up Visits

All study subjects will have follow-up visits at 1, 3 and 6 Months after Baseline to evaluate the joint pain score and to assess adverse events.

The subject should be contacted at least 48 hours prior to their scheduled assessments to be reminded of the required assessment (and applicable wash out period) and to schedule the date and time of contact. At least three documented attempts will be made to contact the subject in order to accomplish maximum subject compliance with the follow-up schedule.

The following tests will be performed at the follow-up visits at 1, 3 and 6 months.

7.6 Follow-up Visits (\pm 7 days)

- Assess Concomitant Medications
- Assess Non- drug therapies
- Assessment of Adverse Events
- Confirm Rescue Medication Washout
 - If subject did not complete medications washout, reschedule the visit to allow washout to be completed.
- Assess Rescue Medication usage
- Collect and assess subject diary
- Patient Global Assessment (PGA)
- Lequesne Hip index and contralateral joints
- Index & Contralateral Hip, Knee and Ankle Joint Pain on Walking (NRS)

- Physical Exam of Index and Contralateral Hip, Knee and Ankle Joints

8. SAFETY PROCESSES

Safety of the subjects participating in this clinical investigation will be monitored throughout the clinical investigation using the Adverse Event (AE) reporting process in the EDC system, to identify real and potential safety issues.

Adverse events will be reported according to the ISO 14155:2011, while recognizing and following the requirements including reporting timelines specified in other specific laws, regulations, directives, standards and/or guidelines as appropriate and as required by the countries in which the study is conducted.

All AEs that occur during or after injection will be recorded. Worsening of a condition that existed prior to the study injection should be recorded as an AE. At each assessment during the trial, AEs that have occurred since the previous assessment must be recorded. All subjects will be questioned and evaluated for AEs or complications associated with the procedure. Complications of the injection include, but are not necessarily limited to: pain, swelling, erythema, bleeding and/or infection at the injection site. The Investigator will determine the severity and relationship of each event, as defined above.

AEs observed during the course of this study, regardless of severity or relationship to the device and/or the procedure will be recorded on the CRF. Each reported complication/AE will also include the duration, action taken to address the AE, and the resolution status (e.g. ongoing, resolved). These subjects will continue to be evaluated for safety at all scheduled follow-up points.

8.1 Definition of Adverse Events

Adverse Device Effect (ADE)

Adverse event related to the use of an investigational medical device.

Note 1: This definition includes adverse events resulting from insufficient or inadequate instructions for use, deployment, implantation, installation, operation, or any malfunction of the investigational medical device.

Note 2: This definition includes any event resulting from the use error or intentional misuse of the investigational medical device.

Adverse Event (AE)

Any untoward medical occurrence, unintended disease or injury or untoward clinical signs (including an abnormal laboratory finding) in subjects, users or other persons whether or not related to the investigational medical device.

Note 1: This includes events related to the investigational medical device or the comparator.

Note 2: This includes events related to the procedures involved.

Note 3: For users or other persons this is restricted to events related to the investigational medical device.

Device Deficiencies (DD)

The inadequacy of a medical device with respect to its identity, quality, durability, reliability, safety or performance.

Note: Device deficiencies include malfunctions, use errors, and inadequate labeling.

Device deficiencies that did not lead to an adverse event but could have led to a medical occurrence

- a) if either suitable action had not been taken,
- b) if intervention had not been made, or
- c) if circumstances had been less fortunate,

shall be reported under the same conditions as a serious adverse event.

Malfunction

Failure of an investigational medical device to perform in accordance with its intended purpose when used in accordance with the instructions for use or Clinical Investigation Plan.

Serious Adverse Events (SAE)

An adverse event that:

- a) led to a death,
- b) led to a serious deterioration in the health of the subject user or other persons that either resulted in:
 - 1) a life-threatening illness or injury, or
 - 2) a permanent impairment of a body structure or a body function, or
 - 3) in-patient or prolonged hospitalization. or
 - 4) medical or surgical intervention to prevent life threatening illness or injury or permanent impairment to a body structure or a body function.
- c) led to foetal distress, foetal death or a congenital abnormality or birth defect

Note: A planned hospitalization for pre-existing condition or a procedure required by the protocol without a serious deterioration in health is not considered to be a serious adverse event.

Serious Adverse Device Effects (SADE)

An Adverse Device Effect that has resulted in any of the consequences characteristic of a serious adverse event.

Anticipated Serious Adverse Device Effect (ASADE) is an effect which by its nature, incidence, severity or outcome has been identified in the risk analysis report.

Unanticipated Serious Adverse Device Effects (USADE)

A Serious Adverse Device Effect which by its nature, incidence, severity or outcome has not been identified in the current version of the risk analysis report.

8.2 Safety Reporting Process – principal investigator responsibilities

The principal investigator shall report all adverse events and device deficiencies in the appropriate sections of the e-CRF and provide where requested by the sponsor, the necessary clinical or technical information that may contribute to clarifying the circumstances.

The principal investigator shall report all serious adverse events (SAEs) and device deficiencies (DDs) that might have led to a SAE: if a) suitable action had not been taken or b) intervention had not been made or c) if circumstances had been less fortunate, to the sponsor within 24 hours after knowledge of the event using the appropriate e-CRF.

When required by national or local regulations, the principal investigator shall also notify the EC/IRB and Regulatory Agencies of all reportable events according to national regulations within the by regulations required timelines and may also be requested by the EC/IRBs to provide annual reports. The principal investigator shall document all adverse events and device deficiencies in the e-CRF from the point of enrollment until the subject is exited from the study.

8.3 Information provided by the clinical investigation site

The principal investigator will provide the following information, at a minimum, for each adverse event (AE) or Adverse Device Effect (ADE):

- Date of the AE or ADE.
- Date Principal Investigator (or authorized designee) became aware of AE or ADE
- Description of AE or ADE, relevant diagnostic findings
- Treatment
- Resolution
- Assessment of:
 1. severity of the event
 - a. Mild: asymptomatic or mild symptoms; clinical or diagnostic observations only; intervention not indicated.
 - b. Moderate: minimal, local or noninvasive intervention indicated; limiting
 - c. Severe: medically significant but not immediately life-threatening; hospitalization or prolongation of hospitalization indicated; disabling
 - i. Life-threatening: urgent intervention indicated, disabling
 - ii. Fatal: death related to AE
 2. relationship of the event to the investigational device (related, unlikely related, possible related, probable related or causal relationship)
 3. relationship of the event to the index procedure (related, unlikely related, possible related, probable related or causal relationship)
 4. causality

- a. disease under study
- b. lack of performance of the investigational device or comparator/worsening of treated condition
- c. medical history
- d. concomitant or previous medication
- e. other (specify)

The principal investigator will supply the sponsor and/or designee, with any additional information related to the safety reporting of a particular event upon request.

The sponsor is responsible for the classification of all adverse events and ongoing safety evaluation of the clinical investigation and shall:

1. Review the investigator's assessment of all adverse events and determine and document in writing their seriousness, severity and relationship to the investigational device; in case of disagreement between the sponsor and the principal investigator(s), the sponsor shall communicate both opinions to concerned parties.
2. Review all device deficiencies and determine and document in writing whether they could have led to a serious adverse device effect; in case of disagreement between the sponsor and the principal investigator(s), the sponsor shall communicate both opinions to concerned parties.
3. Ensure the reporting to the Ethics Committee (EC) by the principal investigator(s), of all serious adverse events and device deficiencies that could have led to a serious adverse device effect, if required by national regulations or by the EC.
4. Review and report all reportable events (including device deficiencies) according to national regulations in acceptable timely conditions and shall monitor for increased incidence and severity.
5. Ensure that the EC or other applicable regulatory authorities are informed of significant new information about the clinical investigation, and
6. In case of serious adverse device effects and device deficiencies that could have led to serious adverse device effects, determine whether corrective or preventive action is required.

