6.3 Exploratory Endpoints

Any comparisons across timepoints (baseline to 6 months) not described in the primary or secondary endpoints, including but not limited to:

- Demographics
- Medical History
- History of joint osteoarthritis
- Rescue Medication Use
- Treatment Failure
- Injection procedure
- Concomitant medications
- Non-drug therapy

6.4 Safety Endpoint:

The incidence, severity, and relationship to treatment of all Adverse Events (AE) will be collected from the treatment injection to the 6 month assessment.

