7.3.9.3 Concomitant Medications

A medication is considered concomitant if taken after signing the ICF and up to and including the last follow-up assessment. Data on medications will include: medication name, dose, unit, route, frequency, start date, stop date, indication and whether the medication was taken for an AE.

At each study assessment, the subject will be asked about any new medications that were started since the last assessment. Indications for any new medications started after the study treatment will be recorded as AEs, unless the medications are administered for a pre-existing condition.

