9.2.2 Adverse Events

Subjects with AEs will be summarized with frequencies and percentages by system organ class and preferred term, severity, and relationship to investigational product/procedure. In summaries of AEs by severity and relationship to investigational product/procedure, subjects reporting multiple episodes will be counted once under the worst severity and the strongest relationship, respectively. Serious Adverse Events will also be presented by relationship to investigational product/procedure.

Adverse events occurring prior to the index treatment will not be recorded in this trial.

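### The AE relationship scale in section 8.3 has no level for an unrelated event, for either device or procedure; its first level is probably a slip

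*Protocol*

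**What the plan says.** Section 8.3 lists the minimum information for each adverse event. Item 2 is the "relationship of the event to the investigational device (related, unlikely related, possible related, probable related or causal relationship"). Item 3 is the "relationship of the event to the index procedure (related, unlikely related, possible related, probable related or causal relationship"). The two lists are identical.

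Other sections determine which events must be rated and how the ratings are used:

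- **Section 8:** adverse events "regardless of severity or relationship to the device and/or the procedure will be recorded on the CRF". It also says: "The Investigator will determine the severity and relationship of each event, as defined above".
- **Section 8.1:** the definition of an adverse event covers occurrences "in subjects, users or other persons whether or not related to the investigational medical device". An adverse device effect is then defined as an adverse event that is related to use of the device.
- **Section 7.3.9.3:** "Indications for any new medications started after the study treatment will be recorded as AEs, unless the medications are administered for a pre-existing condition".
- **Section 6.4 (safety endpoint):** "The incidence, severity, and relationship to treatment of all Adverse Events (AE) will be collected".
- **Section 9.2.2:** in the summaries by severity and by relationship, "subjects reporting multiple episodes will be counted once under the worst severity and the strongest relationship, respectively". Serious events are also tabulated by relationship.

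**The concern.** The protocol requires unrelated events to be recorded and then rated, but the rating scale has no place for them. Such events are to be expected over six months. Under section 7.3.9.3, starting a new medicine for a condition that did not exist before generates an adverse event whatever its cause. Section 4.2 lists upper respiratory tract infection and back pain from the knee programme apart from the events related to injection.

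If the eCRF copies the printed list, one of two things follows:

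1. Sites code unrelated events as *unlikely related*, the lowest level that is not a positive statement. *Not related* and *unlikely* are then merged and cannot be separated later. The counts for possible, probable and causal are unaffected.
2. Some sites read *related* by its position, as the bottom of the scale, and others by its meaning, as the top. One label then holds opposite judgements.

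The second outcome is the more damaging. Relationship is part of the safety endpoint, and safety in the hip is one of the two things the study sets out to show. An analysis plan cannot recover a distinction that was never collected.

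**Working it through.** The check is mainly textual. No sample size, power or alpha calculation enters it.

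**Step 1. Read the two scales level by level.**

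| Position | Item 2, device | Item 3, procedure | Means *not related*? | Literally asserts a relationship? |
|---|---|---|---|---|
| 1 | related | related | no | yes |
| 2 | unlikely related | unlikely related | no | no |
| 3 | possible related | possible related | no | no |
| 4 | probable related | probable related | no | no |
| 5 | causal relationship | causal relationship | no | yes |

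In each item, 0 of 5 levels mean *not related* and 2 of 5 literally assert a relationship. Both relationship items (2 of 2) are affected.

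**Step 2. Look for another scale.** The protocol has none. Section 8 says severity and relationship are defined above that point, but both are set out only later, in 8.3. The only graded terms earlier on are the frequency categories for known reactions in section 4.2, which concern something else. Item 4 of 8.3 (causality) lists possible causes such as the disease under study, medical history or medication. It can name an alternative cause, but it is not a level of either scale and is not what 9.2.2 tabulates.

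**Step 3. Ask what the first level was meant to be.** Positions 2 to 5 ascend: unlikely < possible < probable < causal. A level printed below *unlikely* should express less than *unlikely*. *Related* expresses more, and it duplicates position 5 in meaning. If it is read as *not related*, the list becomes a complete ascending five-level scale. That reading is an inference; the absence of a *not related* level is not. The same wording in two separate items makes a chance loss in text conversion less likely.

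**Step 4. Apply the scale to the rule in 9.2.2.** Counting a subject under the strongest relationship needs ordered levels. Take a subject with one event coded *related* and another coded *possible related*. By position the subject counts under *possible*; by meaning, under *related*. The printed text does not settle which.

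**Step 5. Weight of one subject.** The synopsis plans 25 treated subjects. One subject whose strongest relationship is miscoded moves 1/25 = 0.040, or 4.0 percentage points, between rows of the relationship table. The 25 is itself worded differently elsewhere (an upper limit in section 6.5, a minimum in section 9.1), so 4.0 points applies to exactly 25.

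**The case against.** The strongest objection is that no harm is shown. Investigators code events in the eCRF, which is not available here, and if its list is correct the effect is zero. Even with the printed list, the first outcome leaves the possible, probable and causal counts unchanged, and no passage shows that sites would really use *related* in opposite senses. The other four levels ascend so plainly that the slip is easy to notice.

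There are also safeguards:

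- Site staff and the monitor review the protocol, CRFs and completion instructions before enrolment (section 12).
- The sponsor provides instructions on uniform assessment and eCRF training (section 13.16).
- Item 4 can flag an alternative cause.
- The sponsor reviews the investigator's assessment of every event and documents its own view of relationship to the device in writing (section 8.3).

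It can also be said that this is a drafting slip and not a deliberate design choice, that 4.0 points is the weight of any single subject in any table of this trial, and that a rank order for a table could be left to the analysis plan.

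Much of this stands, and it is why the point is minor. The size depends on an unseen form, the 4.0 points illustrates scale and is not an effect estimate, and the rank order would be evident once the word is corrected. But none of the safeguards corrects the printed list, and training on the protocol as it stands would teach the faulty one. The sponsor's written determination covers device relationship only, so the procedure scale has no equivalent check. This is also not a detail deferred to the analysis plan: the protocol fixes the collection scale itself, and fixes it wrongly.

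**Conclusion.** The concern holds, as a minor point. Both relationship scales in 8.3 lack a level for unrelated events, although the protocol requires such events to be recorded and rated, and *related* has no determinable rank under the strongest-relationship rule in 9.2.2. That much follows directly from the text. That the first level is a slip for *not related* is a well-supported inference.

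The practical size is unknown. It is zero if the eCRF already offers *not related* in place of the first level. Otherwise each miscoded subject shifts 4.0 percentage points in a table of 25. The protocol gives no adverse event rate, so no count of affected subjects is claimed.

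The efficacy analyses are unaffected. So is the investigator's 24-hour reporting to the sponsor under section 8.2, which depends on seriousness and not on relationship.

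**What to change.** - In section 8.3, items 2 and 3, replace the first level with *not related*, so that the scale runs not related < unlikely < possible < probable < causal.
- In section 9.2.2, refer to that order for the strongest-relationship count.
- In section 8, point the reference for severity and relationship to section 8.3, where both are set out.
- Check that the eCRF list and its completion instructions match the corrected scale. If events have already been coded on the printed list, query every entry of *related* and *unlikely related* with the site before the tables are produced.

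The cost is one word in two places, two short cross-references and a check of the eCRF, plus queries only if the faulty list was used. Design, visits and sample size do not change.

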9. STATISTICAL CONSIDERATIONS

9.1 Sample Size

The primary analysis will be the mean change in index hip pain on walking from baseline to 6 months as measured by the Numerical Rating Scale.

The hypothesis to be tested is:

$$H_0: \mu_{DMON} = 0 \text{ versus } H_A: \mu_{DMON} > 0.$$

In this hypothesis, μ_{DMON} is the mean change in pain on walking from baseline at 6 Months in CINGAL treated patients.

The data will be analyzed via a one sample t-test.

It is assumed that a mean change in pain from baseline of 2 points represents a clinically significant improvement with a standard deviation of 2 - 2.5 points, for 80% power and alpha of 5%

then a total of 15 subjects are required. To ensure sufficient subjects are available at the 6 month follow up, it is proposed to enroll and treat at least 25 subjects which should be more than adequate to demonstrate that treatment of the study population with CINGAL would reduce joint pain at 6 months.

Single sites should not enroll and treat more than 50% of the total enrollment.

9.2 Statistical Methods

Tabulation of summary statistics, graphical presentations, and statistical analyses will be performed. Where not otherwise specified, the last pre-treatment observation will be used as baseline for calculating post-treatment changes from baseline. The primary presentations and analyses will be based on data pooled across study centers. All testing and confidence intervals will use a significance level of 5%.

9.2.1 Demographic and Baseline Characteristics

All demographic and baseline characteristics will be tabulated. Medical history findings, physical examinations and concomitant medications will be tabulated.

9.2.2 Adverse Events

Subjects with AEs will be summarized with frequencies and percentages by system organ class and preferred term, severity, and relationship to investigational product/procedure. In summaries of AEs by severity and relationship to investigational product/procedure, subjects reporting multiple episodes will be counted once under the worst severity and the strongest relationship, respectively. Serious Adverse Events will also be presented by relationship to investigational product/procedure.

Adverse events occurring prior to the index treatment will not be recorded in this trial.

9.2.3 Subject Populations

The Safety Population will be defined as all subjects who undergo Study Treatment, and the safety analysis will be performed on this population.

The primary analysis on the primary endpoint will be performed on the Intent to Treat (ITT) population, defined as all patients who were treated in the study. All Primary and Secondary endpoints will be analyzed using the ITT population.

A secondary analysis will be conducted on the Per Protocol (PP) population. Since the primary endpoint is at 6 Months, this is all subjects who complete the 6 Month assessment and who do not have a major deviation from the protocol. For all other assessments, this is defined as the subjects who complete those assessments according to the protocol.

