Criteria for Evaluation	
Primary Endpoint:
 
 Reduction of index hip Numerical Rating Scale (NRS) pain on walking from baseline to 6 Months post injection. 
Secondary Endpoints:
 
 Improvement in Lequesne Hip index from baseline to 6 months post injection. Improvement in Patient Global Assessment (PGA) from baseline to 6 months post injection. OMERACT-OARSI responder rate in index hip at 6 months post injection. Time to treatment failure Reduction in Medication usage from baseline to 6 months post injection. 
Exploratory Endpoints
 
Any comparisons across timepoints (baseline to 6 months) not described in the primary or secondary endpoints including but not limited to:
 
 Demographics Medical History

	
 • History of joint osteoarthritis • Rescue Medication Use • Treatment Failure • Injection procedure • Concomitant medications • Non-drug therapy 
Safety Endpoint:
 
The incidence, severity, and relationship to treatment of all Adverse Events (AE) will be collected from the first treatment injection to the 6 month assessment.

Statistical Analysis	
The primary analysis on the endpoints will be performed on the ITT (Intent to Treat) populations. All Primary and Secondary endpoints will be analyzed using the ITT population.
 
A secondary analysis will be conducted on the Per Protocol (PP) population. Since the primary endpoint is at 6 months this is all subjects who complete the 6 month assessment and do not have a major deviation in the conduct of the protocol. For all other visits, this is defined as the subjects who complete those visits according to the protocol.
 
All safety analyses will be conducted on all subjects who undergo treatment of Cingal in the hip joint.

Sites	Up to 10 clinical sites in EU
Sponsor	
Anika Therapeutics, Inc. [name], United States of America
 
Phone: + 1 [contact] Fax: + 1 [contact]

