5.2.1 CINGAL WARNINGS

Cingal has the following Warnings and Precautions per its approved labeling:

PRECAUTIONS

General:

- Those precautions normally considered during injection of substances into joints are recommended.
- Appropriate examination of any joint fluid present is necessary to exclude a septic process.
- Only medical professionals trained in accepted injection techniques for delivering agents to joint spaces should inject Cingal for this application.
- The synovial space should not be overfilled.
- If pain increases during the injection procedure, the injection should be stopped and the needle withdrawn.
- A marked increase in pain accompanied by local swelling, further restriction of joint motion, fever, and malaise are suggestive of septic arthritis. If this complication occurs and the diagnosis of sepsis is confirmed, appropriate antimicrobial therapy should be instituted.
- Single Use only; reuse of the contents of the syringe may result in infection and increase occurrence of adverse events.

Triamcinolone hexacetonide

- This product contains a corticosteroid and so should be used with caution in patients suffering from the following conditions:
 - cardiac insufficiency, acute coronary artery disease,
 - hypertension,
 - thrombophlebitis, thromboembolism
 - myasthenia gravis,

- osteoporosis,
- gastric ulcer, diverticulitis, ulcerative colitis, recent intestinal anastomosis,
- exanthematous diseases,
- psychosis,
- Cushing's syndrome,
- diabetes mellitus,
- hypothyroidism,
- renal insufficiency, acute glomerulonephritis, chronic nephritis,
- cirrhosis,
- infections that cannot be treated with antibiotics,
- metastatic carcinoma.

- All corticosteroids may increase calcium excretion.
- The product must not be administered intravenously, intraocularly, epidurally or intrathecally.
- Intra-articular injection should not be carried out in the presence of active infection in or near joints.
- The load on strained joints in particular should be lightened immediately after the injection to avoid overloading.
- If, during treatment, the patient develops serious reactions or acute infections, the treatment must be stopped and appropriate treatment given.

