6.6.4 Baseline Exclusion Criteria

2. Subject has a decrease of ≥ 2 in the NRS pain on walking from Screening to Baseline in the index hip.
3. Subject has a contraindication to continue with the study treatment injection based on the visual appearance of the synovial fluid aspirate.

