7.4 Baseline Visit: Treatment Visit (Day 0)

The Baseline Visit (Day 0) will occur 7 to 14 days after the Screening Visit to allow for rescue medication washout. The injection will occur at this Baseline visit along with the following activities:

Before Treatment Injection

- Concomitant Medications
- Current non-drug therapies
- Confirm Medication Washout
 - If subject did not complete medications washout, reschedule the visit to allow washout to be completed.
- Patient Global Assessment (PGA)
- Lequesne Hip index
- Index & Contralateral Hip, Knee and Ankle Joint Pain on Walking (NRS Scale)
 - Confirm Baseline Inclusion & Exclusion Criteria for NRS pain on walking
- Physical Exam of Index and Contralateral Hip, Knee and Ankle Joints

Treatment Procedure

The Treating Physician may perform the Study Injection to the index hip as standard of care dictates or delegate the injection to qualified study staff.

Intra-articular injection of the index hip joint may be conducted under fluoroscopic or ultrasound guidance as required by standard of care treatment. Guidelines for the injection procedural steps are provided below. Modifications to this technique should be recorded in the CRFs.

- Patient is supine, index hip rotated internally 15-20 deg.
- Prep the skin at injection site with 1% betadine solution or equivalent.
- Peri- articular injection site anesthesia by injection of lidocaine or topical refrigerant anesthetic (e.g. ethyl chloride).
- Fluoroscopic or ultrasound guidance may be utilized if required to insert 18-21 gauge needle anteriorly towards the anterior-inferior joint capsule, approximately 8-10 cm below the inguinal ligament and just below the femoral head, taking care to avoid the femoral artery.
- If using fluoroscopic guidance, a small amount of fluoroscopic contrast agent (0.5 to 1.0 ml) should be injected through the needle to verify intra-articular placement.
- If using ultrasound guidance, a small volume of air (up to 0.5 ml) may be injected to verify IA positioning.
- If pooling of the contrast agent or air around the needle tip is observed, the needle should be repositioned.

- When contrast agent or air is successfully injected into the joint, intra-articular placement is confirmed.
- Following confirmation of intra-articular needle placement, the joint may be aspirated to remove synovial fluid.
 - Confirm the Baseline Exclusion for synovial aspirate.
- 4 ml of CINGAL is injected into the joint.

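### Subjects stopped at the aspirate check have had the injection procedure but no Cingal; they fall outside every analysis set, and the protocol's rules conflict on whether their adverse events are recorded

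*Protocol*

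**What the plan says.** Section 9.2.3 fixes the safety set: "The Safety Population will be defined as all subjects who undergo Study Treatment, and the safety analysis will be performed on this population". It does not define Study Treatment. The synopsis is more specific: "All safety analyses will be conducted on all subjects who undergo treatment of Cingal in the hip joint". ITT in 9.2.3 is likewise limited to treated patients, and PP requires the 6-month assessment or, for other time points, completion of those assessments according to the protocol.

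One baseline exclusion in section 6.6.4 can be judged only once the joint has been entered: "Subject has a contraindication to continue with the study treatment injection based on the visual appearance of the synovial fluid aspirate". Section 7.4 places it accordingly. The listed order is skin preparation, "anesthesia by injection of lidocaine or topical refrigerant anesthetic", insertion of an 18-21 gauge needle, contrast or air depending on the guidance used, and optional aspiration. Then comes "Confirm the Baseline Exclusion for synovial aspirate", and only after that the 4 ml of Cingal.

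On recording, section 9.2.2 says: "Adverse events occurring prior to the index treatment will not be recorded in this trial". Section 6.4 starts collection at the treatment injection, section 8 covers events during or after injection, and section 8.2 has the investigator document events from enrollment onward.

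The protocol treats harms of the procedure as part of safety. The AE definition in 8.1 notes: "This includes events related to the procedures involved". Section 8.3 asks for relationship to the index procedure separately from relationship to the device, and 9.2.2 summarizes AEs by relationship to product or procedure.

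**The concern.** The protocol creates a group of subjects who undergo an invasive joint procedure and then, by its own exclusion rule, receive no Cingal. Section 4.2 lists reactions to the anesthetic and to contrast, infection, and neurovascular, cartilage or bone damage among the risks of hip injection. Several of these can arise before any Cingal is given. If one occurs in a subject stopped at the aspirate check, no analysis population contains that subject, and under 9.2.2 the event might not be recorded at all.

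At stake is how complete the procedure-related safety summary is. The study is meant to support use of the product in a new joint with about 25 treated subjects, so a single procedural event changes what is reported.

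**Working it through.** **Step 1: where the subject stands.** Take a subject whose aspirate meets the exclusion.

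| Question | Protocol source | Result |
|---|---|---|
| Needle in the joint? | 7.4, steps before the check | Yes |
| Local anesthesia? | 7.4 | Yes, lidocaine or a topical refrigerant |
| Contrast or air? | 7.4 | Depends on the guidance used |
| Cingal? | 7.4, step after the check | No |
| Safety Population? | 9.2.3 read with the synopsis | No |
| ITT? | 9.2.3, treated patients | No |
| PP? | 9.2.3, completed follow-up assessments | No |

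**Step 2: whether the event is recorded.** Suppose a reaction to the anesthetic occurs before the aspirate check.

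| Section | Recording starts | Event captured? |
|---|---|---|
| 6.4 | Treatment injection | No |
| 8 | During or after injection | Unclear; depends on whether injection means the whole procedure |
| 8.2 | Enrollment | Yes, if the subject counts as enrolled |
| 9.2.2 | Index treatment | No |

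The four rules do not give one answer. Even where 8.2 applies, Step 1 shows that the event is recorded but belongs to no analysis set.

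**Step 3: size.** The protocol states no figure for this point. The only input it supplies is 25 treated subjects (synopsis). The number stopped before Cingal, k, is an assumption, shown for 1 to 3.

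Share of procedure-exposed subjects left out = k / (25 + k):
- k = 1: 1/26 = 3.8%
- k = 2: 2/27 = 7.4%
- k = 3: 3/28 = 10.7%

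If exactly one procedural event occurs, and it occurs in a stopped subject, the planned set reports 0/25 = 0% (exact 95% CI 0 to 13.7%). A set of all subjects in whom the procedure was started reports:
- k = 1: 1/26 = 3.8% (0.1 to 19.6%)
- k = 2: 1/27 = 3.7% (0.1 to 19.0%)
- k = 3: 1/28 = 3.6% (0.1 to 18.3%)

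**Step 4: direction.** Let x be the number of treated subjects with a procedure-related event and y the number of stopped subjects with one. The planned set reports x/25; the full set gives (x + y)/(25 + k). The count falls by y, so it can be understated and never overstated. The rate is understated only if y/k > x/25. With x = 1, y = 0 and k = 2, the planned rate is 1/25 = 4.0% against 1/27 = 3.7%, so the omission slightly raises it.

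**The case against.** A safety set made up of subjects who received the product is conventional, and an SAP, not shown here, could add a listing for untreated subjects. Study Treatment is undefined in 9.2.3, and 7.4 puts the whole sequence under a treatment-procedure heading, so 9.2.3 alone could be read more widely. Section 8.2 requires AE documentation from enrollment and reporting of SAEs to the sponsor within 24 hours, and section 13.12 seeks safety evaluations from withdrawn subjects. Aspiration is optional, lidocaine can be replaced by a topical agent, and contrast or air depends on guidance, so not every stopped subject has every exposure.

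Much of this stands as a limit on size. It does not close the gap. The synopsis wording settles the narrow reading of the safety set, and an SAP cannot summarize events that the protocol says not to record.

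Three stronger readings are tempting but not supported:
- A reader might infer that the omission can only make the procedure look safer. That holds for the event count, not for the rate (Step 4).
- A reader might add to the omitted group those covered by the precaution in 5.2.1, "If pain increases during the injection procedure, the injection should be stopped and the needle withdrawn". That most naturally describes an injection already under way; such a subject has probably received some Cingal and arguably counts as treated.
- A reader might take 9.2.2 alone as proof that these harms go uncaptured. Section 8.2 says otherwise, so the documents show a contradiction, not a settled failure to record.

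**Conclusion.** The point holds, on the aspirate exclusion alone. Subjects stopped at that check are exposed to the procedure but sit in no analysis population, and four sections disagree on whether their events are recorded. The procedure-related event count can be understated. The direction of any bias in the rate depends on the AE rate in these subjects, which the protocol does not give.

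The number affected is also not given; it is probably small and may be zero. The percentages above rest on assumed values of 1 to 3 stopped subjects beside 25 treated. The conclusion also relies on the synopsis to read Study Treatment as Cingal. The primary analysis is not affected. The change is worth making because the protocol itself fixes both the population and the recording rule, and following them could lose a real procedural harm in a study this small.

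**What to change.** 1. Reconcile the start of AE recording across 6.4, 8, 8.2 and 9.2.2 into a single rule under which AEs are recorded at the latest from the start of the injection procedure (first anesthetic or skin puncture).
2. In 9.2.3 and the synopsis, report procedure-related AEs on all subjects in whom the procedure was started, and list those not given Cingal separately.
3. Keep product-related AEs on Cingal-treated subjects.
4. Leave ITT as it is.

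The cost is a few sentences of protocol text and a small amount of AE follow-up for any subject stopped before Cingal, for whom the protocol currently sets no schedule. Treated subjects have no added visits, and the sample size and primary analysis do not change.
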